6.2. KEY DEFINITIONS

6.2.1. Baseline

Baseline assessment for migraine and headache endpoints will be based upon the data recorded in the eDiary at time 0, prior to the first administration of Investigational Product. Baseline MBS is recorded at Visit 2. For other variables, the baseline assessment will be the latest available valid measurement taken prior to the first administration of Investigational Product.

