6.1.4 Treatment Phase: Up to 12 Months

Visit 3 will be considered the “Day 1” visit for data capture purposes. Subjects will be instructed to complete the eDiary at the time of each suspected migraine attack. Once the eDiary confirms that the migraine qualifies for treatment, the subject will follow the steps provided to self-administer the study drug. If necessary, subjects may return for unscheduled visits for dispensation of additional drug kits.

The following constitutes a migraine that qualifies for treatment with study drug:

- No medication has already been taken to treat the migraine symptoms on the day of the suspected attack before applying M207.
- Presence of at least two of the following characteristics:
 - Unilateral location
 - Pulsating quality
 - Moderate or severe pain intensity
 - Aggravation by or causing avoidance of routine physical activity (e.g., walking or climbing stairs)
- During headache, at least one of the following:
 - Nausea and/or vomiting
 - BOTH photophobia AND phonophobia

The following procedures are to be started at Day 1 after receiving study medication:

- Using the eDiary, the subject will record the following to confirm the headache meets the qualifications for a migraine:
 - Migraine symptoms and pain assessment
- Once the qualifying migraine has been confirmed, subject self-administers the study drug patches. Patches cannot be applied to a previous application site unless the site is free of redness, swelling, and/or bruising. In addition, patches must not be applied to any area where the skin appears tattooed, sunburned, broken and/or irritated.
- Each set of two patches must be applied next to one another (or one above the other), on the same arm. If any skin appears broken or irritated, subsequent doses will be applied a few inches away from the previously applied patches on the same arm (or both patches on the other arm) to avoid applying in an irritated area.
- Qualifying migraine attacks cannot be treated any earlier than 48 hours after the time of patches application for a previously treated migraine attack.
- Subject will continue to record the following in the eDiary at specified time points as follows:
 - Migraine symptoms and pain assessment at the time of treatment, 30 minutes, 2 hour, 12 hours, 24 hours, and 48 hours post patch application
 - Subject reported skin assessment for bleeding at 30 minutes only

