APPENDIX 3 – eDiary Questions

Most Bothersome Symptom (To be completed when site is setting up the eDiary for the subject)

- Ask the subject what his/her most bothersome symptom is. This is the symptom other than pain that is most bothersome most of the time with their migraine. (Sick to their stomach, sensitive to light, sensitive to sound/noise)

Run-in Period Diary, Nightly Questions (Start the evening of Visit 2)

- Did you have a headache in the past 24 hours? (Yes, No)
- *If No is answered for bullet one question*
 - Did you experience excessive yawning today? (Yes, No)
 - Did you experience mood changes today? (Yes, No)
 - Did you experience excessive fatigue (tiredness) today? (Yes, No)
- *If yes, please answer the following questions based on your headache symptoms in the last 24 hours:*
 - How bad was your headache pain at its worst? (Mild, Moderate, Severe)
 - Was the headache pain on only one side of your head? (Yes, No)
 - Was the headache pulsating (throbbing)? (Yes, No)
 - Did activity make your headache get worse? (Yes, No)
 - Were you nauseated (sick to your stomach)? (Yes, No)
 - Did you vomit (throw up)? (Yes, No)
 - Did light bother you? (Yes, No)
 - Did sound or noise bother you? (Yes, No)
 - Did you take any medication to treat your headache? (Yes, No)

Migraine Treatment Diary (Starts at Day 1 when subject feels he/she is experiencing a migraine attack)

Please fill in your diary when you feel you are experiencing a migraine attack

- Are you currently experiencing a migraine attack? (Yes, No)
- How bad is your headache pain? (Mild, Moderate, Severe)
- Is the headache pain on only one side of your head? (Yes, No)
- Is the headache pulsating (throbbing)? (Yes, No)
- Does activity make your headache pain get worse? (Yes, No)
- Are you nauseated (sick to your stomach)? (Yes, No)
- Did you vomit (throw up)? (Yes, No)
- Does light bother you? (Yes, No)
- Does sound or noise bother you? (Yes, No)
- Have you taken any medication to treat your headache? (Yes, No)
- Were you experiencing an aura (e.g., flickering light, flashes, or spots) at the start of headache? (Yes, No)
- What day and time did your headache start? (Today, Yesterday) Choose time
- Did you wake up with this headache? (Yes, No)
- eDiary confirms whether this is a qualified migraine and instructs subject to apply the patches:
- *If a non-qualifying migraine:*

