4. ENDPOINTS

4.1. EFFICACY ENDPOINTS

- Proportion of Migraines that are pain free at 30 minutes, 2 hours, 12 hours, 24 hours, and 48 hours post-dose
- Proportion of subjects with pain freedom at 30 minutes, 2 hours, 12 hours, 24 hours, and 48 hours post-dose for the 1st, 5th, 15th, and 25th migraine a subject experiences
- Proportion of migraines with most bothersome other symptom freedom at 30 minutes, 2 hours, 12 hours, 24 hours, and 48 hours post-dose
- Proportion of subjects with most bothersome other symptom freedom at 30 minutes, 2 hours, 12 hours, 24 hours, and 48 hours post-dose for the 1st, 5th, 15th, and 25th migraine a subject experiences
- Proportion of migraines with pain relief at 30 minutes, 2 hours, 12 hours, 24 hours and 48 hours post-dose
- Proportion of migraines with nausea freedom at 30 minutes, 2 hours, 12 hours, 24 hours and 48 hours post-dose
- Proportion of migraines with photophobia freedom at 30 minutes, 2 hours, 12 hours, 24 hours and 48 hours post-dose
- Proportion of migraines with phonophobia freedom at 30 minutes, 2 hours, 12 hours, 24 hours and 48 hours post-dose
- Proportions of migraines that require rescue medication within 2 hours post-dose
- Proportion of migraines that recurred within 24 and 48 hours post-dose
- Proportion of migraines with sustained pain freedom from 2 to 24 hours post-dose and from 2 to 48 hours post-dose
- Frequency of responses on the migraine assessment of current therapy (ACT)

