8.1.4. The Proportion of Migraines with Pain-Relief

In addition to all above, the proportion of migraines with pain relief without rescue medication use (improvement of pain severity to mild or none from moderate or severe at baseline, or to none from mild at baseline) at 30 minutes, 2 hours, 12 hours, 24 hours, and 48 hours after dosing will also be summarized descriptively.

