17. INDEX OF TABLES

Table Number	Table Title
14.1.1.1.1	Reasons for Screen Failures and Run-In Failures All Subjects
14.1.1.1.2	Subject Disposition All Subjects
14.1.1.2	Protocol Deviations Safety Population
14.1.1.3	Demographics and Baseline Characteristics Safety Population
14.1.1.4	Migraine History Safety Population
14.1.1.5	Medical History by System Organ Class and Preferred Term Safety Population
14.1.1.6	Prior Medications Safety Population
14.1.1.7	Concomitant Medications Safety Population
14.1.1.8	Study Drug Exposure Safety Population
14.2.1.1.1	Summary of Pain Freedom at 30 Minutes and 2, 12, 24, and 48 Hours Postdose Over All Migraine Attacks Modified Intent-to-Treat Population
14.2.1.1.2	Summary of Subjects with Pain Freedom at 30 Minutes and 2, 12, 24, and 48 Hours Postdose by Migraine Number Modified Intent-to-Treat Set
14.2.1.2.1	Summary of Freedom from Most Bothersome Symptom (MBS) at 30 minutes, 2 hours, 12 hours, 24 hours, and 48 hours Postdose over all Migraine Attacks and MBS Modified Intent-to-Treat Population
14.2.1.2.2	Absence of Most Bothersome Symptom (MBS) at 30 Minutes and 2, 12, 24, and 48 Hours Postdose by Migraine Number and MBS Modified Intent-to-Treat Population
14.2.1.3	Summary of Freedom from Nausea, Photophobia, and Phonophobia, 30 Minutes and 2, 12, 24, and 48 Hours Postdose Over All Migraine Attacks Modified Intent-to-Treat Population
14.2.1.4	Pain Relief at 30 Minutes and 2, 12, 24, and 48 Hours Postdose Over All Migraine Attacks Modified Intent-to-Treat Population
14.2.1.5	Use of Rescue Medication within 2 Hours Postdose Over All Migraine Attacks Modified Intent-to-Treat Population
14.2.1.6.1	Sustained Pain Freedom from 2 to 24 Hours Postdose Over All Migraine Attacks Modified Intent-to-Treat Population
14.2.1.6.2	Sustained Headache Pain Freedom from 2 to 48 Hours Postdose Over All Migraine Attacks Modified Intent-to-Treat Population
14.3.1.1	Overview of Treatment Emergent Adverse Events Safety Population
14.3.1.2a	Treatment Emergent Adverse Events by System Organ Class and Preferred Term - ALL Adverse Events Safety Population

Table Number	Table Title
14.3.1.2b	Treatment Emergent Adverse Events by System Organ Class and Preferred Term - E-Diary Skin Assessment Reported Adverse Events Safety Population
14.3.1.2c	Treatment Emergent Adverse Events by System Organ Class and Preferred Term - Other Subject Reported Adverse Events Safety Population

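### The SAP ties the migraine baseline to the first dose in the study, so followed as written it mis-scores pain relief in some later attacks

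*SAP*

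**What the plan says.** SAP section 6.2.1 has one rule for migraine and headache endpoints: baseline comes from "data recorded in the eDiary at time 0, prior to the first administration of Investigational Product". Two sentences later it uses the same anchor for everything else: "For other variables, the baseline assessment will be the latest available valid measurement taken prior to the first administration of Investigational Product".

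Three other places in the SAP make pain relief an attack-level quantity that depends on baseline:

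- Section 4.1 lists the endpoint as "Proportion of migraines with pain relief at 30 minutes, 2 hours, 12 hours, 24 hours and 48 hours post-dose".
- Section 8.1.4 defines relief, in attacks without rescue medication, as "improvement of pain severity to mild or none from moderate or severe at baseline, or to none from mild at baseline".
- Section 17 plans Table 14.2.1.4 as "Pain Relief at 30 Minutes and 2, 12, 24, and 48 Hours Postdose Over All Migraine Attacks".

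Section 13 records the move from subjects to migraines as the unit of analysis but mentions no matching change to baseline.

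In the protocol, section 6.1.4 lets a headache qualify on "Presence of at least two of the following characteristics". Moderate or severe pain is only one of the four listed, so a mild attack can qualify. The same section collects "Migraine symptoms and pain assessment at the time of treatment" for each treated attack, and the pre-dose pain question in Appendix 3 offers mild, moderate and severe as answers.

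**The concern.** A subject may treat many attacks over up to 12 months, but section 6.2.1 supplies one baseline per subject. For every attack after the first, the relief rule would then compare post-dose pain with how bad a different headache was.

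Two errors follow. An attack that starts mild and stays mild counts as relief if the first attack was moderate or severe. An attack that falls from moderate or severe to mild counts as a failure if the first attack was mild.

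The study has no control arm, so an error of this kind is not offset by the same error in a comparator. It goes straight into the reported percentage. A programmer who follows the text and one who assumes a per-attack baseline would also produce different versions of Table 14.2.1.4, each with some support in the SAP.

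**Working it through.** The plan states no figure on this point, and SAP section 3.5 gives the sample size no statistical basis, so there is nothing of the plan's own to reproduce.

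**Step 1: which attacks change status.** Take an attack without rescue medication. Cross first-attack pre-dose pain (3 levels), the attack's own pre-dose pain (3) and post-dose pain (4): 3 × 3 × 4 = 36 combinations. Apply the section 8.1.4 rule with each baseline. The result differs in four:

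| First attack, pre-dose | This attack, pre-dose | This attack, post-dose | As written | Own baseline |
|---|---|---|---|---|
| mild | moderate | mild | no relief | relief |
| mild | severe | mild | no relief | relief |
| moderate | mild | mild | relief | no relief |
| severe | mild | mild | relief | no relief |

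The other 32 agree. A moderate-versus-severe mismatch changes nothing.

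**Step 2: can it occur?** With mild pain, two of the remaining three characteristics (unilateral, pulsating, aggravated by activity) must be present. Four of the eight patterns meet this, so a mild attack qualifies if the associated-symptom condition is also met. Section 8.1.4 itself provides for mild pain at baseline.

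**Step 3: inputs for size, at 2 hours.**

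- *m*, share of attacks mild at dosing: assumed 0.05 to 0.40.
- *q*, chance that such an attack is still mild at 2 hours: assumed 0.20 to 0.60.
- *r*, chance that a moderate or severe attack is mild at 2 hours: 0.805 − 0.415 = 0.390. This is 2-hour pain relief (protocol section 1.2.2.3) minus 2-hour pain freedom (protocol Table 4) for 3.8 mg in the earlier study. It assumes that all those subjects started at moderate or severe pain.
- *ρ*, within-subject correlation of mild status: assumed 0 or 0.5.

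**Step 4: formulas, per later attack.**

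- Share whose mild/non-mild status differs from the first attack: *d* = 2*m*(1 − *m*)(1 − *ρ*)
- Mis-scored: (*d*/2)(*q* + *r*)
- Net change in the relief rate: (*d*/2)(*q* − *r*)

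**Step 5: results with *ρ* = 0.**

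- *m* = 0.05: *d*/2 = 0.0475. With *q* = 0.20, mis-scored = 0.0475 × 0.590 = 2.8%.
- *m* = 0.40: *d*/2 = 0.24. With *q* = 0.60, mis-scored = 0.24 × 0.990 = 23.8%.
- Net at *m* = 0.40: 0.24 × (0.20 − 0.390) = −4.6 points; 0.24 × (0.60 − 0.390) = +5.0 points. The sign changes at *q* = 0.39.

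With *ρ* = 0.5 everything halves: 1.4% to 11.9% mis-scored, net −2.3 to +2.5 points. A simulation of 100,000 subjects with 12 or 24 attacks each returned the same mis-scored shares, which checks the algebra and not the assumptions.

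**Step 6: without a mild share.** Set *d* = 0.10. Mis-scored = 0.05 × 0.590 to 0.05 × 0.990, or 3.0% to 5.0% of later attacks. Net = −1.0 to +1.0 points. This still uses the assumed range for *q*.

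**Step 7: other assumptions.** With *m* from 0.05 to 0.30, *ρ* of 0 or 0.5, *q* from 0.20 to 0.50 and *r* from 0.20 to 0.40 (four pairs of *q* and *r*), about 1% to 17% of later attacks are mis-scored and the net shift runs from about −2 to +4 points.

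**The case against.** The best reply is that a per-attack baseline was meant. Time 0 reads naturally as the moment of dosing in a given attack, and section 6.2.1 gives migraine endpoints their own rule, separate from the other variables. SAP section 8.1.5 refers to initial treatment where the unit is the migraine, so the SAP does elsewhere use first-dose wording for an attack's own dose. Section 8.1.4 speaks of improvement, and an attack that starts and stays mild has not improved. The table shells, a separate document, may settle the matter.

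This makes the per-attack intention plausible, but it does not correct the stated anchor. A migraine gets a single dose (SAP section 3.3), and section 11.1 counts one dose whether one or two patches are applied, so a first administration has no natural meaning within an attack. Section 6.2.3 likewise anchors study day to the first administration in the study. A derivation rule belongs in the SAP's key definitions and should not have to be inferred from shells.

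The objections on size largely stand. The mild share, its persistence and the correlation are assumptions, and changing them changes the range. The 23.8% needs the highest mild share, the highest persistence and no within-subject correlation at once. The table reports a proportion, so the net shift matters more than the mis-scored share. An attack with rescue medication fails under either baseline and cannot be mis-scored.

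**Conclusion.** The concern holds. Followed as written, section 6.2.1 gives some second and later attacks the wrong pain-relief status: 4 of the 36 severity combinations, two as false relief and two as missed relief.

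The net shift in the 2-hour rate for later attacks is at most about 5 points in either direction under the assumptions above, and about half that with a correlation of 0.5. Its sign cannot be known in advance. First attacks are unaffected, so the shift in the pooled table is slightly smaller.

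The reach is narrow. Pain freedom, sustained pain freedom, recurrence and rescue use do not depend on baseline severity. Pain relief is descriptive and serves the secondary objective, and no test, error rate or safety result changes. The point should be corrected because the definition is wrong as it stands and cheap to put right. It does not threaten the study's main conclusions.

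**What to change.** Replace the first sentence of SAP section 6.2.1 with wording such as: *For each treated migraine, baseline is the eDiary entry at time 0 of that migraine, before its own patch application.* The Visit 2 declaration of the most bothersome symptom and the rule for other variables can stay as they are.

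Then confirm that the derivation code and the shell for Table 14.2.1.4 use each attack's own time-0 entry.

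The cost is one sentence and a code check. No new data are needed, because pain is already recorded at the time of treatment for every attack. If per-attack scoring was always intended, the sentence only puts that on record.

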If during the run-in period, additional information becomes available to exclude the subject (e.g., return of 12-lead ECG or lab results), the subject should be notified of screen failure and instructed to return any provisional eDiary device (if applicable) to the center.

The run-in period is to determine eligibility for treatment with study medication based on daily eDiary data collection, and is planned to be 2 weeks in duration but may be extended up to an additional 1 week to accommodate scheduling, and/or to confirm diary compliance and eligibility. The run-in period will be a minimum of 14 days and no more than 21 days in duration. Qualified subjects will receive study medication at Day 1 (Visit 3) for up to twelve months for the treatment of migraine headaches. Migraines will be treated with a single dose, consisting of two patches, but subjects can treat multiple migraine attacks throughout the 12 months. Using the eDiary to confirm they are experiencing a qualified migraine, subjects will self-administer the patches and continue to respond to questions in the eDiary for 48 hours post treatment administration.

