4.5 Study Drug Kit Administration, Dispensation, Accountability, and Return

The study drug will be dispensed only to qualified subjects included in this study in accordance with the eligibility criteria specified in the study protocol.

Throughout the study, upon eDiary confirmation of each migraine qualifying for treatment, subjects will self-administer the study drug. Study personnel will train subjects on how to apply the patches with the M207 applicator.

The study physician or designee will record the CTM kit numbers dispensed to each subject on the drug accountability record. The designated site monitor will periodically check the supplies of CTM to ensure accountability of used applicators and unused kits. If necessary, subjects may return for unscheduled visits for dispensation of additional drug kits. Subjects should be

instructed to bring all unused patches to every clinic visit. Returned patches may be re-dispensed for use to the same subject; however, all patches must be accounted for on the drug accountability log as returned and re-dispensed. The number of patches dispensed at each visit, date dispensed, the number of patches used, and the number of returned unused patches at each visit will be documented. Any discrepancies between the ‘actual’ number of patches returned versus the ‘expected’ number to be returned will be explained. If a subject did not apply both patches to treat a migraine, the site must document the reason in the subject’s source record.

Final study drug accountability will be completed after the last subject visit. All drug accountability records will be filed in the site file and TMF as appropriate.

At the end of the study, all unused study drug kits and used and unused applicators will be inventoried and returned as per the sponsor’s instructions.

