 - Subject reported skin assessment for bruising, swelling, and/or redness (at 30 minutes, 2 hours, 12 hours, 24 hours and 48 hours post patch administration time points only)
 - Subject reported skin pain and skin itching at 48 hours post patch administration
- Dispense the Subject Skin Grading Card (Appendix 4) with the eDiary and instruct the subject to refer to this card when grading their skin reaction(s)/symptom(s) in the eDiary. The Grading Card will include a subject reminder to contact the study physician if he/she experiences any serious or severe skin reaction(s) at any time point or for worsening or non-resolving reactions at approximately 3 days post patches application (at 72 hours). In addition, the eDiary will remind the subject to call the study physician if he/she experiences any skin reaction(s) and/or symptom(s) at the patch application site which worsens rather than improves over approximately a five-day period. If the subject

contacts the study physician at any time point for worsening or non-resolving reactions, the subject must be seen for an unscheduled visit. The skin reaction(s)/symptom(s) will be assessed, recorded as an adverse event in the eCRF and followed to resolution.

6.1.5 Month 1 (Visit 4), Month 2 (Visit 5), Month 3 (Visit 6), Month 6 (Visit 7)

Visits must be scheduled to occur on (or within ± 7 days) of the protocol specified study day, ie, on study days 28 (Month 1), 56 (Month 2), 84 (Month 3), and 168 (Month 6). The following procedures will be performed at each visit:

- Administer the Migraine Assessment of Current Therapy (Migraine-ACT) which is completed by the subject
- Collect any unused patches, perform accountability, and dispense patches with applicator
- Perform physical exam, (Month 6 only) (height does not need to be recorded)
- Record vital signs: temperature, respiratory rate (RR), blood pressure (BP), and heart rate (HR)
- Collect urine for urine pregnancy test for all WOCBP
- Collect urine for drug abuse testing (Month 6 only)
- Perform 12-lead electrocardiogram (ECG) (Month 6 only)
- Ensure subject is dispensed the Subject Skin Grading Card (to be used with eDiary entries).
- Collect and review subject's eDiary data with the subject for the following:
 - Subject compliance with study drug treatment and subject responses in eDiary

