4.2. SAFETY ENDPOINTS

- Changes from baseline in physical examination findings at Months 6 and 12
- Changes from baseline in vital signs at Months 1, 2, 3, 6, 9, 12, and at the 2-week post-study visit
- Changes from baseline in clinical laboratory parameters at Month 12
- Changes from baseline and/or shifts in 12-lead ECG parameters at Months 6 and 12
- Frequency of concomitant medications

- Incidence of treatment-emergent systemic and skin AEs (TEAEs)
- Frequencies of type of redness, severity of swelling, amount of bruising, and amount of bleeding (30 minutes only) at the application site as reported by the subject at 30 minutes, 2 hour, 12 hour, 24 hour, and 48 hours post-dose
- Frequencies of amount of skin itching and severity of pain at the application site as reported by the subject at 48 hours post-dose
- Frequencies of amount of bruising, erythema, and edema at the application site as assessed by the Investigator at Months 1, 2, 3, 6, 9, 12, and at the 2-week post-study visit
- Proportion of subjects with presence of skin signs and symptoms as assessed by the Investigator at Months 1, 2, 3, 6, 9, 12, and at the 2-week post-study visit

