6.4. VISIT WINDOWS

Nominal Visits will be used in the analyses as reported on the eCRF. As per section 6.1, the subjects who withdraw/drop out from the study will have their ET visit data collected included in the analysis based on the closest visit window.

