8.1.8. Migraine-ACT Questions (Assessment of Current Therapy)

The frequencies and percentages will be provided for all subject responses on the ACT by visit. Note that if a subject has not treated any migraine attacks since the most recent in clinic study visit, the ACT response will be missing. Missing data will not be imputed.

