11.2.2. Investigator Skin Assessments

The investigator skin assessment will be made at each in clinic visit starting at month 1. The entire surface area of the outer upper arm from the upper shoulder to the elbow will be assessed for the following skin signs or symptoms.

Investigator reported skin bruising, skin redness (erythema), and skin swelling (edema) at the application site will be collected and will also be recorded in the eCRF.

The amount of bruising, erythema, and edema and the presence of skin signs and symptoms will be categorized and assessed as follows:

Skin signs or symptoms	Indicate arm assessed: Subject's Left and/or Right (circle)
Blisters or pustules?	Present: Yes or No If Yes, describe:
Scaly or flakey skin?	Present: Yes or No If Yes, describe:
Erosions or open sores?	Present: Yes or No If Yes, describe:
Scarring?	Present: Yes or No If Yes, describe:
Hyperpigmentation or Hypopigmentation?	Present: Yes or No If Yes, describe:

Bruising assessments (visual rating) will be performed using the following ratings:

Symptom	Rating (circle)
M207 application sites have bruising spots?	0 (clear) = None 1 (mild) = ≤ 25% Present in the upper arm region of all M207 applications 2 (moderate) = ≥ 26 to ≤ 50% Present in the upper arm region of all M207 applications 3 (severe) = > 50% Present in the upper arm region of all M207 applications

Erythema Severity Categories:

Symptom	Rating (circle)
Skin Erythema	0 (clear) = None 1 (mild) = ≤ 25% Present in the upper arm region of all M207 applications 2 (moderate) = ≥ 26 to ≤ 50% Present in the upper arm region of all M207 applications 3 (severe) = > 50% Present in the upper arm region of all M207 applications

Edema Severity Categories:

Symptom	Rating (circle)
Skin Edema	0 (clear) = None 1 (mild) = ≤ 25% Present in the upper arm region of all M207

	
applications
 
2 (moderate) = ≥ 26 to $\leq 50\%$ Present in the upper arm region of all M207 applications
 
3 (severe) = $> 50\%$ Present in the upper arm region of all M207 applications

--	---

The frequencies of amount of bruising, erythema, and edema at the application site as assessed by the Investigator at Months 1, 2, 3, 6, 9, 12, and at the 2-week post-study visit will be summarized. The proportion of subjects with any amount of all 3 symptoms (erythema, edema, and bruising) and all combinations of the 3 symptoms will be summarized by time point.

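### Subjects who attend Month 1 before their first patch are counted as on treatment in the by-visit investigator skin table, which slightly dilutes the Month 1 rates

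*SAP*

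**What the plan says.** **Dosing and visit timing.** Protocol 3.1 places dispensing at Visit 3: "Qualified subjects will receive study medication at Day 1 (Visit 3) for up to twelve months for the treatment of migraine headaches". Protocol 4.5 gives the trigger for dosing: "upon eDiary confirmation of each migraine qualifying for treatment, subjects will self-administer the study drug". Protocol 6.1.4 treats Visit 3 as Day 1, and Protocol 6.1.5 and Table 10 fix Month 1 at Day 28 ± 7. Nothing makes the Month 1 visit depend on an earlier patch.

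**Which records are summarised.** SAP 6.4 states: "Nominal Visits will be used in the analyses as reported on the eCRF". SAP 6.1 likewise confines summary tables to nominal scheduled visits. SAP 5.1 admits to the Safety Population anyone who ever applied a patch, whenever that was.

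**Skin.** SAP 11.2.2 states: "The investigator skin assessment will be made at each in clinic visit starting at month 1". Table 14.3.2.3 reports these ratings by visit in the Safety Population.

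**Vital signs.** For variables other than migraine and headache, SAP 6.2.1 says that "the baseline assessment will be the latest available valid measurement taken prior to the first administration of Investigational Product", with no cap at Visit 3. SAP 4.2 lists as an endpoint "Changes from baseline in vital signs at Months 1, 2, 3, 6, 9, 12, and at the 2-week post-study visit", and Protocol 7.3.2 plans summaries of change at each visit. SAP 11.4 and the index of tables plan listings only.

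**The one place that foresees an interval without dosing.** SAP 8.1.8 says of Migraine-ACT that "if a subject has not treated any migraine attacks since the most recent in clinic study visit, the ACT response will be missing". Skin ratings and vital signs have no matching rule.

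**The concern.** Month 1 is the first on-treatment point in the by-visit series of investigator skin findings, and long-term safety is the primary objective. A subject with no patch yet cannot have a reaction caused by M207. Such a subject adds to the Month 1 denominator but not to the reaction-caused numerator, so the Month 1 rates are pulled toward clear skin. By later visits almost everyone has been exposed, so a little of any rise after Month 1 would come from who is counted and not from repeated use.

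For vital signs, the same record would serve as baseline and as the Month 1 value, so the change would be zero by construction.

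**Working it through.** **Step 1: trace one subject.** The subject receives patches at Visit 3, attends Month 1 on Day 28 and applies the first patch on Day 30.

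- *Population:* in the Safety Population, because a patch was eventually applied (SAP 5.1).
- *Visit label:* Month 1, as reported on the eCRF (SAP 6.4).
- *Skin:* ratings completed that day count in the Month 1 column of Table 14.3.2.3.
- *Vital signs:* the Day 28 reading is the latest before first dose, so it is baseline (SAP 6.2.1). It is also the Month 1 value (SAP 4.2). Change = x − x = 0.
- *Study day:* SAP 6.2.3 counts from first administration, so Day 28 becomes study day −2. The record can be recognised as pre-dose, but no selection rule uses that.

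**Step 2: are such subjects plausible?** Entry allows as few as 2 migraines per month (Protocol 3.2.2), and run-in requires one qualifying attack in 14 days (3.2.4). An attack does not qualify if medication was already taken for it that day (6.1.4). The rule on fewer than 6 qualifying migraines in 12 weeks says only that subjects may be withdrawn (3.2.6.1), and its 12 weeks end after Month 1.

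**Step 3: size.** The plan states no figure to reproduce. Assume treated attacks follow a Poisson process at r per 28 days. Visit 3 is Day 1, so 20, 27 and 34 days have elapsed at Days 21, 28 and 35.

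Fixed rate: f = exp(−r × days/28).

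| r per 28 days | Day 21 | Day 28 | Day 35 |
|---|---|---|---|
| 2 | 24.0% | 14.5% | 8.8% |
| 3 | 11.7% | 5.5% | 2.6% |
| 4 | 5.7% | 2.1% | 0.8% |
| 8 | 0.3% | 0.04% | 0.01% |

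Rates spread evenly over 2 to 8, with c = days/28: f = [exp(−2c) − exp(−8c)] / (6c).

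- Day 28 (c = 0.964): (0.1454 − 0.0004)/5.786 = 2.5%, about 6 of the 250 planned to enter treatment.
- Day 21: 5.5%, about 14 of 250. Day 35: 1.2%, about 3 of 250.

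Sensitivity at Day 28, rates 2 to 8:

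- If 75% of attacks are treated: 5.4%, about 13 of 250. If 50%: about 12.5%, or 31 of 250.
- Among subjects with at least 6 attacks in 84 days, multiply the fixed-rate f by P(≥ 6 in the last 57 days)/P(≥ 6 in 84 days): 5.9% at r = 2. Averaging numerator and denominator over rates 2 to 8 gives 1.4%.

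**Step 4: effect.** If undosed subjects are rated clear, a reaction-caused rate p becomes p(1 − f). For illustration only, Protocol Table 9 shows investigator-rated erythema in 19 of 83 subjects (22.9%) after one 3.8 mg treatment, on a different scale. That would become 22.9 × 0.975 = 22.3% at f = 2.5%, and 22.9 × 0.855 = 19.6% at f = 14.5%.

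**Step 5: later visits.** At r = 2, Day 56 gives exp(−2 × 55/28) = 2.0%, and Day 168 gives exp(−2 × 167/28) ≈ 0.0007%. Post-baseline ECG and physical examination start at Month 6 and laboratory tests are repeated at Month 12, so those endpoints are in practice untouched.

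**The case against.** The strongest reply is that little in the planned output is exposed.

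- **Vital signs.** A reader might infer that a planned table will show a distorted Month 1 change. It will not: SAP 11.4 lists all values and flags abnormal ones by fixed cut-offs that do not use baseline, and the index has no vital-sign table. Even if a change were summarised, Protocol 1.2.1 reports that Phase 1 blood pressure in the M207 groups was near baseline at 1 hour, and clinic visits are not timed to dosing. Diluting a change with no stated reason to differ from zero matters little. This stands, and is why the vital-sign effect is secondary.
- **Skin.** A reader might infer that the unexposed arm always enters the table, or that the baseline rule puts it there. Neither is established. The route is SAP 5.1 with 6.1 and 6.4, not 6.2.1. Protocol 6.1.5 directs the examination to the arm where patches have been applied, so some sites may leave the form blank. Against that, SAP 11.2.2 and Protocol 6.2.13.1 call for the whole outer upper arm at every clinic visit from Month 1. The documents do not settle it, so f is an upper limit, under the model, on what reaches the table.
- **Other dermal evidence.** The eDiary skin tables are tied to actual applications, and treatment-emergent events are defined relative to treatment. Both are unaffected.
- **Size.** The attack rates and the Poisson form are assumptions. This stands.

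What remains is that an explicit visit rule includes these records and no rule removes them.

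**Conclusion.** The gap is real and small. As written, the plan counts Month 1 skin ratings made before any patch as on-treatment findings in one planned table, 14.3.2.3, wherever sites complete the form. It also allows a zero vital-sign change by construction in the SAP 4.2 endpoint and in any summary made under Protocol 7.3.2.

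On the Poisson assumption, with every attack treated, the Month 1 dilution is about 2.5% for rates spread over 2 to 8 per 28 days. It is 14.5%, 5.5% and 2.1% at fixed rates of 2, 3 and 4, and larger if a good share of attacks goes untreated. It further assumes that undosed arms are rated clear.

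A reader might infer that a rise in skin findings after Month 1 would be explained by this alone. At these sizes the documents do not support that, and the study's overall safety conclusions are not in question. This is a clarification worth making because it costs almost nothing.

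**What to change.** Keep the baseline rule in SAP 6.2.1 and add to SAP 6.1 or 6.4:

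> By-visit post-baseline summaries of investigator skin assessments, and of vital-sign changes if summarized, include only subjects whose first patch application (eDiary date and time) was before the visit assessment; earlier records are listed and the number excluded at each visit is shown. A record used as baseline is not also counted as post-baseline.

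Using time as well as date keeps subjects who applied a patch earlier on the visit day. If the clock time of the clinic assessment is not captured, a convention for same-day cases is needed.

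The cost is two sentences and one filter. SAP 11.1 already takes first dose dates from the eDiary. Month 1 n falls by a few percent under most of the assumptions above, and the Month 1 column then leans slightly toward subjects with more frequent attacks, which the displayed number excluded makes visible. No data are lost, because the earlier records are listed.
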